5.6. Safety Analyses

All safety analyses will be performed for each cohort using the All Treated Population, unless otherwise specified.

5.6.1. Extent of Exposure

5.6.1.1. Administration of Study Drug

The following parameters will be summarized:

- Duration of treatment
- Number of cycles treated
- Number of doses received
- Cumulative dose
- Relative dose intensity

Duration of treatment (days) will be calculated as follows: 1) calculate the date of the last dose – date of first dose + 1 for each treated cycle; 2) sum up across all treated cycles.

Cumulative dose is the sum of the doses administered to a subject during the treatment period.

Relative dose intensity will be calculated as cumulative dose (dose received) divided by dose planned (taking the dosing cycle into consideration)

A by-patient listing of dosing of study drug and listing of batch number will be also provided.

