4.4. Discontinuation of Treatment

A patient will be discontinued from all study drug for any of the following reasons:

1. Disease progression
2. Unacceptable AEs, or change in underlying condition such that the patient can no longer tolerate therapy, as evidenced by a dose delay >28 days from the scheduled start date of the next cycle or need for more than 2 dose reductions outlined in this protocol
3. Physician's decision, including need for other anticancer therapy not specified in the protocol or surgery or radiotherapy to the only site(s) of disease being followed in the study
4. Pregnancy
5. Termination of the study by the Sponsor
6. At the patient's request at any time irrespective of the reason

Patients who withdraw consent for further treatment may choose to remain on study; in such a case, all study evaluations should continue as outlined in this protocol. If the patient withdraws consent to all follow-up assessments, the patient should be considered to have discontinued the study as described in Section 4.5.

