5. STUDY TREATMENT

5.1. Study Drug Administration

A study cycle is defined as 28 days. Futibatinib is supplied as 4 mg tablets and will be taken orally at a dose of 20 mg daily until the patient meets any of the administration discontinuation criteria (see Section 4.4).

Futibatinib should be administered under fasting conditions. It should be taken with a glass of water, on an empty stomach, at the same time each day. No food should be consumed for 2 hours prior and 1 hour after the dose of futibatinib, but patients may drink water during this period.

When a PK sample is collected, futibatinib should be administered on site after collection of the first PK sample.

In the event of a dosing delay up to 12 hours after the scheduled dosing time, the patient should still take that day's dose. If the dosing delay continues for >12 hours after the scheduled dosing time, or if the patient vomits after a dose, the patient should skip dosing for that day and not make up for it the following day.

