3. STUDY DESCRIPTION

3.1. Summary of Study Design

This study is an open-label, multinational, 3-arm Phase 2 study evaluating the efficacy, safety, tolerability, pharmacokinetics (PK), and pharmacodynamics of futibatinib in patients with *FGFR* aberrations. Eligible patients will be assigned to 1 of 3 treatment cohorts based on diagnosis and *FGFR* gene aberration status (Figure 1):

Abbreviations: FGFR=fibroblast growth factor receptor; n=number of patients planned; QD=daily

Figure 1: Study Design Flow Chart

Patients will receive futibatinib at an oral dose of 20 mg once a day on a continuous 28-day cycle.

Treatment will continue until disease progression, unacceptable toxicity, or any other of the criteria for treatment discontinuation is met. For patients who discontinue treatment for reasons other than disease progression, tumor assessments should be continued until disease progression is documented or until initiation of subsequent new anticancer therapy (whichever occurs first).

Patients will be followed for survival every 12 weeks (± 2 weeks) until survival events (deaths) have been reported for 75% of enrolled patients, the patient withdraws consent, or the study is terminated early by the Sponsor.

Additional cohorts may be added in the future in the case of new emerging data. This change will be implemented through a protocol amendment which will describe the rationale for the addition(s).

Table 1. Schedule of Events (Cohorts A and B)

Evaluation	Treatment Period (1 cycle = 28 days)						Notes					
	Cycle 1		Cycle ≥2									
Screening (Within 28 days of 1 st dose)		D1 (±3 days)		D8 (±3 days)		D15 (±3 days)	D22 (±3 days)	D1 (±3 days)	D22 (±3 days)	D1 (±3 days)	D22 (±3 days)	Written informed consent will be obtained prior to any study-related assessments or procedures.
Written informed consent	X											
Review eligibility criteria	X											
Demographics/medical history	X											
Review of baseline signs and symptoms	X											
Prior & concomitant medications, AE assessments												
Physical examination	X	X					X		X		X	
Vital signs	X	X					X		X		X	
Height and weight	X	X					X		X		X	
ECOG performance status	X	X					X		X		X	
12-Lead electrocardiogram	X	X					X		X		X	
Hematology	X	X	X	X	X	X	X	X	X	X	X	
Coagulation	X	X	X	X	X	X	X	X	X	X	X	
Chemistry (serum or plasma)	X	X	X	X	X	X	X	X	X	X	X	

Evaluation	Treatment Period (1 cycle =28 days)				Notes	
	Cycle 1		Cycle ≥ 2			
	D1 (± 3 days)	D8 (± 3 days)	D15 (± 3 days)	D22 (± 3 days)		

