4. STUDY PERIODS AND POPULATIONS FOR ANALYSIS

4.1. Study Periods for Analyses

Study periods are defined in [Table 6](#) and shown in [Figure 2](#).

Table 6: Definition of Study Periods for Analysis

Period	Definition
Screening Period (Baseline)	The Screening Period is defined as the time from when the patient signs the Informed Consent Form (ICF) until the date of first dose of futibatinib.
Treatment Period	The treatment period is the time from first dose of futibatinib (Day 1) to the date of last dose of futibatinib.
Safety Assessment Period	The Safety Assessment Period begins at the time the ICF is signed and continues until at least 30 days after the last dose of futibatinib.
On-treatment Period (This period will be used for safety analyses)	On-treatment Period is the time from the first dose of futibatinib (Day 1) to 30 days after the last dose of futibatinib. Unless otherwise specified, the On-treatment Period will be the basis for safety analyses.

[figure not shown]

Figure 2: Study Periods for Analysis

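### The SAP's cycle-by-cycle duration of treatment drops off-drug days at a cycle boundary but counts those inside a cycle, and the planned dose for relative dose intensity is left undefined

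*SAP*

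**What the plan says.** SAP section 5.6.1.1 lists duration of treatment, cycles treated, number of doses, cumulative dose and RDI. Duration is the last dose date minus the "date of first dose + 1 for each treated cycle; 2) sum up across all treated cycles". Cumulative dose is separate: "Cumulative dose is the sum of the doses administered to a subject during the treatment period". RDI also has its own formula: "Relative dose intensity will be calculated as cumulative dose (dose received) divided by dose planned (taking the dosing cycle into consideration"). Planned dose is not defined further.

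SAP section 4.1, Table 6, describes the period without removing gaps: "The treatment period is the time from first dose of futibatinib (Day 1) to the date of last dose of futibatinib". Protocol section 3.3.2 defines it the same way.

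On dosing, SAP section 3.1 states "Patients will receive futibatinib at an oral dose of 20 mg once a day on a continuous 28-day cycle", and protocol section 5.1 states "A study cycle is defined as 28 days". Protocol section 4.4 ends treatment for "a dose delay >28 days from the scheduled start date of the next cycle", so shorter delays to a next cycle are foreseen. Protocol section 5.2 allows dosing to resume when the criteria are met within 28 days of the last dose.

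Protocol section 11.5.2 asks for total duration of administration, without a formula, and for both actual and relative dose intensity. The SAP lists only the relative one. SAP section 5.6.2.7 divides adverse event counts by an exposure time that it does not define.

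**The concern.** A per-cycle sum suits a regimen with planned rest periods. Here there are none, so a gap between the last dose of one cycle and the first dose of the next is a hold or a delay. The rule removes such a gap from the total, yet keeps a gap of the same length that lies between two doses of one cycle. Two patients with equal holds can then have different durations because of where the hold fell, and for a boundary hold the figure is shorter than the Treatment Period in the same SAP.

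Duration of treatment will be read as time under treatment. It may also become the denominator of the exposure-adjusted event rates. RDI sits next to it with a planned dose that can be read in several ways, so the choice would fall to the programmer.

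**Working it through.** The documents give no exposure or RDI figure to reproduce, so the SAP formulas are applied to constructed dosing calendars.

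**Inputs from the documents:** 20 mg once daily; 28-day cycles; holds and delays of up to 28 days possible. **Assumptions:** one hold of 7 to 28 days, two or six cycles, no dose reduction. The documents give no frequency, length or timing of holds.

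**Formulas**
- SAP duration = sum over cycles of (last dose day − first dose day + 1)
- Elapsed duration = last dose day of the study − first dose day + 1
- Cumulative dose = 20 mg × dosing days
- RDI = cumulative dose / planned dose

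**A 14-day hold over two cycles**
- (a) Inside cycle 1, off drug on days 8 to 21. Cycle 1 runs from day 1 to 28 and cycle 2 from day 29 to 56. SAP duration 28 + 28 = 56; elapsed 56; dosing days 14 + 28 = 42.
- (b) Straddling the boundary on a fixed calendar, off drug on days 22 to 35. Cycle 1 doses on days 1 to 21 and cycle 2 on days 36 to 56. SAP duration 21 + 21 = 42; elapsed 56; dosing days 42.
- (c) Cycle 2 delayed. Cycle 1 doses on days 1 to 28 and cycle 2 on days 43 to 70. SAP duration 28 + 28 = 56; elapsed 70; dosing days 56.

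The SAP figure equals elapsed time in (a) and days on drug in (b) and (c). Over six cycles the same hold gives 168 against 168 elapsed in (a), 154 against 168 in (b), and 168 against 182 in (c).

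**RDI for the two-cycle case under three readings of planned dose**

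| Planned dose | (a) 840 mg received | (b) 840 mg received | (c) 1120 mg received |
|---|---|---|---|
| 20 mg × 28 × cycles started | 840/1120 = 75% | 840/1120 = 75% | 1120/1120 = 100% |
| 20 mg × SAP duration | 840/1120 = 75% | 840/840 = 100% | 1120/1120 = 100% |
| 20 mg × elapsed duration | 840/1120 = 75% | 840/1120 = 75% | 1120/1400 = 80% |

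**Range for holds of 7 to 28 days**
- Duration falls short of elapsed time by 7 to 28 days when the hold is at a boundary. Over two cycles that is 11% (7/63, delayed) to 50% (28/56, straddling). Over six cycles it is 4% (7/175) to 17% (28/168).
- RDI in case (c), where the first two readings give 100%: the elapsed reading gives 56/63 = 89% to 56/84 = 67% over two cycles, and 168/175 = 96% to 168/196 = 86% over six.
- If the SAP duration is the event-rate denominator, such a patient's rate is multiplied by elapsed/SAP duration: 63/56 = 1.13 to 56/28 = 2.00 over two cycles, and 175/168 = 1.04 to 168/140 = 1.20 over six.

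**The case against.** Four objections carry weight.

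**RDI.** A reader might infer that the duration rule overstates dose intensity. The documents do not support that. RDI is cumulative dose over planned dose, and duration is not named as an input. RDI is overstated if planned dose is built on the summed duration, or on 28 days per started cycle when cycles shift with a delay. It is right if planned dose follows elapsed time, or 28 days per cycle on a fixed calendar. In the shifted-cycle case the fault would lie in the planned-dose definition, not the duration rule. What stands is that the denominator is undefined.

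**Exposure.** A reader might also infer that exposure is understated for every patient with a delay. That is true only against first-to-last-dose time, and only for holds touching a boundary. As days on drug, the boundary cases are exact (42 = 42, 56 = 56), and the in-cycle hold is the one overstated (56 against 42). Number of doses and cumulative dose are unaffected.

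**Table 6.** It defines study periods, not the duration statistic, so this is a mismatch between two descriptions of treatment time and not a strict contradiction. Safety analyses rest on the On-treatment Period, which the rule does not alter.

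**Visibility.** Holds are not hidden. SAP section 5.6.1.2 summarises and lists interruptions and reductions, section 5.6.2.4 tabulates the adverse events behind them, and dosing is listed by patient.

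None of this rescues the rule, which still gives 56 days for a hold inside a cycle and 42 for the same hold across a boundary.

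**Conclusion.** The point holds for duration of treatment: the stated rule gives a figure that is not consistently elapsed time or days on drug, and for boundary holds it is shorter than the SAP's own Treatment Period. This is so whether cycles keep a fixed calendar or shift with the delay. For one hold of 7 to 28 days at a boundary, the shortfall against elapsed time is 11% to 50% over two cycles and 4% to 17% over six.

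For RDI the conclusion is conditional. With 28 days of planned dose per started cycle and cycles that shift, a 7- to 28-day delay over six cycles shows 100% against 96% to 86%. With planned dose based on elapsed time there is no overstatement. The documents do not settle which applies.

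It would also go too far to say that the rule systematically flatters the drug: if this duration feeds the event rates, it raises them.

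The effect is confined to descriptive exposure summaries and, if they use this duration, the exposure-adjusted event rates. The primary endpoints are unaffected. The trial-wide size cannot be computed, because the frequency and timing of holds are not given.

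The absence of actual dose intensity from the SAP list is a plain omission. Amendment 1 of the protocol already required it in section 11.5.2, so an older protocol version does not explain the gap, and SAP section 6 declares no changes to the planned analyses.

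**What to change.** In SAP section 5.6.1.1:
- Define duration of treatment as date of last dose minus date of first dose + 1 over the whole treatment period, in line with Table 6. Report the number of dosing days separately if time on drug is wanted.
- Define planned dose for RDI as 20 mg × that duration, which also settles delayed and incomplete cycles.
- Add actual dose intensity, as mg per day over the same duration.

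In SAP section 5.6.2.7, state that the exposure-time denominator is this same duration.

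The cost is a few sentences and a simpler program, with no new data. RDI may look slightly less favourable for patients with delayed cycles. The change will not make RDI identical for equal holds: in the two-cycle example it is 75% for the in-cycle hold and 80% for the delayed cycle, because the second patient received 56 doses and not 42. That difference is real.

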5.6.1.2. Modification of Study Drug

The number and percentage of patients with at least one dose interruption along with reason for the interruptions will be summarized.

The number and percentage of subjects with at least one dose reduction and reason for the dose reduction will be summarized.

The number and percentage of subjects with at least one dose discontinuation and reason for the dose discontinuation will be summarized.

By-patient listings of dose interruption, dose reduction, and dose discontinuation will be also provided.

5.6.2. Adverse Events

5.6.2.1. Deaths

On-treatment deaths and reasons for death will be summarized.

A by-patient listing of all deaths occurring during screening, on treatment, 30-day safety follow-up, or survival follow-up periods will be provided.

5.6.2.2. Adverse Events

An AE is any untoward medical condition that occurs in patients while participating in this clinical trial. AEs will be coded according to the MedDRA (the most up-to-date version at the time of analysis) terminology and the severity of the toxicities will be graded according to NCI CTCAE Version 5.0, where applicable.

A treatment-emergent AE (TEAE) is defined as an AE that is starting or worsening at the time of or after the first dose of study drug administration and within 30 days after the last dose of study drug, and does not necessarily have a causal relationship to the use of the study drug.

In this study, only TEAEs will be summarized. Note that all collected AEs, including TEAEs, will be presented in listings as described in Section 5.1.

The following summary tables will be generated:

1. Summary of AEs with the number and percentage of patients reporting AEs, serious AEs, grade ≥ 3 AEs, AEs leading to study drug discontinuation, interruption and dose reduction, and AEs with the outcome of death.
2. Summary of treatment-related AEs with the number and percentage of patients reporting AEs, serious AEs, grade ≥ 3 AEs, AEs leading to study drug discontinuation, interruption and dose reduction, and AEs with outcome of deaths.
3. Summary of AEs by worst CTC Grade (grade 1, 2, 3, 4, 5, any grade, Grade ≥ 3) presented by SOC and Preferred Term (PT).
4. Summary of TEAEs by worst CTC grade (Grade 1, 2, 3, 4, 5, any grade, Grade ≥ 3) presented by SOC and PT.
5. Grade ≥ 3 AEs by worst CTC Grade (grade 3, 4, 5, 3-5) presented by SOC and PT.
6. Grade ≥ 3 TEAEs by worst CTC Grade (grade 3, 4, 5, 3-5) presented by SOC and PT.
7. Summary of AEs leading to death by SOC and PT.
8. Summary of the most common AEs ($\geq 10\%$ incidence) and median time to first AE by SOC and PT.

5.6.2.3. Adverse Events Leading to Discontinuation of Study Drug

AEs leading to discontinuation will be summarized:

- Summary of AEs leading to discontinuation of study drug by worst CTC Grade (grade 1, 2, 3, 4, 5, any grade, Grade ≥ 3) presented by SOC and PT
- Summary of TEAEs leading to discontinuation of study drug by worst CTC grade (Grade 1, 2, 3, 4, 5, any grade, Grade ≥ 3) presented by SOC and PT

A by-patient listing of AEs leading to discontinuation of study drug will also be provided.

5.6.2.4. Adverse Events Leading to Dose Modification of Study Drug

AEs leading to dose modification (including dose interruption and reduction) of study drug will be summarized:

- Summary of AEs leading to dose modification of study drug by worst CTC Grade (grade 1, 2, 3, 4, 5, any grade, Grade ≥ 3) presented by SOC and PT
- Summary of TEAEs leading to dose modification of study drug by worst CTC grade (Grade 1, 2, 3, 4, 5, any grade, Grade ≥ 3) presented by SOC and PT

A by-patient listing of AEs leading to dose modification of the study drug will also be provided.

5.6.2.5. Serious Adverse Events

Serious adverse events (SAEs) will be summarized:

- Summary of SAEs by worst CTC Grade (grade 1, 2, 3, 4, 5, any grade, Grade ≥ 3) presented by SOC and PT
- Summary of treatment-related SAEs by worst CTC Grade (grade 1, 2, 3, 4, 5, any grade, Grade ≥ 3) presented by SOC and PT

A by-patient listing of SAEs will also be provided.

5.6.2.6. Adverse Events of Special Interest

Incidence

Adverse events of special interest (AESIs) will be summarized:

- Summary of AESIs with the number and percentage of patients reporting AESIs, serious AESIs, grade ≥ 3 AESIs, AESIs leading to study drug discontinuation, interruption and dose reduction, and AESIs with the outcome of death.
- Summary of AESIs by worst CTC grade (grade 1, 2, 3, 4, 5, any grade, Grade ≥ 3) presented by category or subcategory / PT

A by-patient listing of AESI will also be provided.

Time to Onset

Time-to-onset of selected AESI (eg, hyperphosphatemia) will be graphically displayed using the Kaplan-Meier technique.

- Time-to-onset of any grade AESI
- Time-to-onset of Grade ≥ 3 AESI

The derivation of time-to-onset of AESI is detailed in Section 7.4.

Time to Resolution

Time-to-resolution of selected AESI (eg, hyperphosphatemia) will be summarized.

- Time-to-resolution of Grade ≥ 3 AESI

The following summary statistics will be reported: percentage of subjects who experienced the specific events, percentage of subjects with resolution of the AESI (clustered), median, 1st quartile and 2nd quartile of time-to-resolution along with 95% CI (derived from Kaplan-Meier estimation) and ranges.

Time-to-resolution of Grade ≥ 3 AESI (eg, hyperphosphatemia) will be graphically displayed using the Kaplan-Meier technique.

Time-to-resolution analyses are restricted to patients who experienced the specific events. Collapsing selected AE and derivation of time-to-resolution of AESI is detailed in Section 7.5.

5.6.2.7. Multiple Events

The following summary tables will be provided:

- A table showing the total number and rate (exposure adjusted) of occurrences for all AEs by SOC and PT
- A table showing the total number and rate (exposure adjusted) of occurrences for AESI by category / subcategory

The exposure adjusted incidence rate per X patient time is calculated as $X \times Y \times (\text{total number of unique AEs}) / (\text{total exposure time})$, where:

- $X = \text{user-specified time factor, } X = 1000 \text{ or } 100$
- $Y = 365.25 \text{ for years or } Y = 30.4375 \text{ for months}$

For example, Incidence rate per 100 person-years of exposure (IR/100 P-Y) is calculated as $100 \times 365.25 \times (\text{total number of unique AE count}) / (\text{total exposure time in days})$.

Unique instances of all AEs (that is, after duplicates have been eliminated and overlapping and contiguous occurrences of the same event (same PT) have been collapsed) will be summarized (0 event, 1 event, 2-3 events, ≥ 4 events) by PT. Unique instances of AESI will be summarized (0 event, 1 event, 2-3 events, ≥ 4 events) by category/subcategory.

Unique instances of all AEs will be listed.

The algorithm of collapsing selected AE records is detailed in Section 7.5.

5.6.3. Clinical Laboratory Evaluations

Clinical laboratory results will be summarized using SI units. Laboratory measurements will be summarized for each parameter. Descriptive statistics (n, mean, standard deviation, median, minimum and maximum) will be presented for clinical chemistry, hematology, and coagulation parameters at each scheduled visit. Change from baseline will be summarized in a similar manner.

Laboratory test results will be graded by NCI CTCAE (Version 5.0). Shift tables will be presented for each laboratory parameter to display the shift from baseline grade to the worst post-baseline grade. Summary tables will be provided presenting the number and percentage of patients for each laboratory test by baseline grade and worst post-baseline grade. All post-baseline assessments (including unscheduled visits) will be used to determine the worst post-baseline grade. Time to maximum Grade 3/4 and time to resolution (return to grade ≤ 2 or baseline grade or below) may be summarized as appropriate.

All clinical laboratory data will be presented in by-patient listings.

The laboratory tests of hematology, coagulation, serum chemistry are listed in [Table 18](#).

Table 18: Laboratory Tests

Assessment	Test Items
Hematology and Coagulation	Red blood cell count, hemoglobin, hematocrit, platelets, white blood cell count with differential (absolute neutrophil count, lymphocytes, monocytes, eosinophils, basophils), Prothrombin time-international normalized ratio, Activated partial thromboplastin time, fibrinogen
Chemistry (Serum or plasma)	AST, ALT, alkaline phosphatase, total bilirubin, direct bilirubin, albumin, lactate dehydrogenase, inorganic phosphorus, triglyceride, total cholesterol, creatinine, urea or blood urea nitrogen, sodium, potassium, chloride, calcium (corrected value), magnesium, blood glucose, creatinine clearance (if there is a measured value, use the measured value)

For a calculated creatinine clearance (Ccr) value, use the Cockcroft-Gault formula:

Male Ccr (mL/min) = weight (kg) × (140-age(years)) / [72 × serum creatinine (mg/dL)]

Female Ccr (mL/min) = male Ccr × 0.85

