11.5.4. Safety Analyses

The safety analysis will be performed using the All Treated Population.

Adverse events will be coded according to the Medical Dictionary for Regulatory Activities terminology and the severity of the toxicities will be graded according to the NCI-CTCAE V5.0, where applicable.

Concomitant medications will be coded according to the WHO Drug Dictionary for Concomitant Medication.

All AEs will be summarized (by incidence) and listed by the System Organ Class, preferred term, toxicity/severity grade, and causal relationship to futibatinib. In addition, separate summaries of SAEs and Grade 3 or 4 AEs will be presented.

For all AEs that occurred between the patient providing documented informed consent and the last day of the Safety Follow-up Period, lists of preferred AE terms, grade, onset date, actions, outcome of AE, date of outcome confirmed, causalities with the study drug, and comments on AEs will be listed by patient.

Hematological and chemistry laboratory parameters will be graded according to the NCI-CTCAE V5.0 where applicable. The worst severity grade, time to maximum Grade 3 or 4 value, and time to resolution (return to baseline grade or below) will be summarized.

Safety data (AEs and clinical laboratory results) will be summarized descriptively. A list of 12-lead electrocardiogram findings will be presented by patient.

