3.3. Determination of Sample Size

A total of approximately 115 patients will be enrolled in the study.

Approximately 60 patients with solid tumors harboring *FGFR* rearrangements will be enrolled in Cohort A. Sample size considerations (primary endpoint ORR) are based on a 2-stage Simon design (Simon, 1989), comparing a poor response of $\leq 10\%$ vs a promising response of $\geq 25\%$, at a 5% 1-sided significance level and approximate 90% power.

- In Stage 1 (futility assessment), enrollment will include 35 patients and accrual will continue to Stage 2, if at least 4 (11.4%) of 35 patients respond (CR or PR).
- In Stage 2, if the Stage 1 futility boundary is exceeded, an additional 25 patients will be enrolled, for a total of approximately 60 patients. With a total of 60 patients, if the observed ORR is 30%, the 95% exact confidence interval (CI) is 18.9%, 43.2%.

Table 3: Observed ORR with Exact 95% CI (Cohort A)

ORR	95% Exact Confidence Interval
20%	[10.8% - 32.3%]
25%	[14.7% - 37.9%]
30%	[18.9% - 43.2%]

Approximately 35 patients with gastric or GEJ cancer harboring *FGFR2* amplification will be enrolled in Cohort B. Sample size considerations are based on differentiating a historical control ORR of 10% or less, with a target ORR of 35%. Assuming the true ORR is 35%, the cohort has approximately 96% power to reject the null hypothesis that the true ORR is $\leq 10\%$, considering a 2-sided alpha of 5%. With a sample size of 35, observing at least 8 responders will have a 95% CI lower bound excluding 10% (ORR of 23% with 95% CI [10.4% - 40.1%]).

Table 4: Observed ORR with Exact 95% CI (Cohort B)

ORR	95% Exact CI
23%	[10.4% - 40.1%]
29%	[14.6% - 46.3%]
37%	[21.5% - 55.1%]

Approximately 20 patients with MLNs harboring *FGFR1* rearrangements will be enrolled in Cohort C. Sample size considerations are based on differentiating a historical control CR rate of 10% or less, with a target CR rate of 50%. Assuming the true CR rate is 50%, the cohort has over 95% power to reject the null hypothesis that the true CR rate is $\leq 10\%$, considering a 2-sided alpha of 5%.

Observing at least 6 responders out of 20 treated patients will have a 95% CI lower bound excluding 10% (CR rate of 30% with 95% CI [11.9% - 54.3%]).

Table 5: Observed CR Rate with Exact 95% CI(Cohort C)

CR Rate	95% Exact Confidence Interval
30%	[11.9% - 54.3%]
40%	[19.1% - 64.0%]
50%	[27.2% - 72.8%]

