6. CHANGES IN PLANNED ANALYSIS

There have been no changes to the initially planned analyses as of the finalization of this SAP.

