7.5. Time-to-Resolution Definition

In order to derive the time-to-resolution, overlapping or contiguous AESIs within a specific category will be collapsed into what will be termed “clustered” AESIs. For example, if a patient (without pre-treatment AE) experienced an AE from 01 January to 05 January, another AE (with different PT but within same category) from 06 January to 11 January, and the same AE from 10 January to 12 January, these will be collapsed into one clustered AESI from 01 January (onset date) to 12 January (resolution date). [Table 20](#) summarizes key derivation steps for each type of clustered select AEs.

Time-to-resolution of AESI (any grade) for a specific category is defined as the longest time from onset to complete resolution or improvement to the grade at baseline among all AESI clusters in this category experienced by patients. Events which worsened into Grade 5 events (death) or have a resolution date equal to the date of death are considered unresolved. If a clustered AESI is considered to unresolved, the resolution date will be censored to the last known date that the patient was alive. Improvement to the grade at baseline implies that all different AE events in the clustered AESI should at least have improved to the corresponding (that is, with same preferred term) baseline grade (or improve to a lower grade). Time-to-resolution is defined only for patients who experienced at least one AESI in the specific category.

The time-to-resolution of AESI (Grade 3-5) for a specific category is defined similarly, with an onset date corresponding to a Grade 3-5 AESI.

Time-to-resolution of drug-related AESI (any grade or Grade 3-5) is defined similarly but restricted to drug-related AESIs.

Time-to-resolution for a specific subcategory is defined similarly but restricted to events of this subcategory.

Table 20: Derivation of Clustered AESIs

Type of clustered select AE	Derivation
Any grade	Collapse any on-treatment AESI from the same category

Type of clustered select AE	Derivation
Drug-related of any grade	Collapse any on-treatment drug-related AESI from the same category
Grade 3-5	Collapse any on-treatment AESI from the same category. Resolution will be based on the onset date of the earliest Grade 3-5 records (clusters with only Grade 1-2 should not be selected)

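### SAP 5.6.3 adds Grade 2 or lower as an alternative route to laboratory resolution and makes the summary optional, while the protocol requires return to baseline grade and commits to reporting it; no change is declared

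*SAP*

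**What the plan says.** Protocol 11.5.4, in the current Amendment 2, says of laboratory parameters: "time to resolution (return to baseline grade or below) will be summarized". The current synopsis has the same definition and the same commitment, and so does Section 11.5.4 of Amendment 1.

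SAP 5.6.3 defines resolution as "return to grade ≤ 2 or baseline grade or below". The full clause makes the summary optional: "time to resolution (return to grade ≤ 2 or baseline grade or below) may be summarized as appropriate". The same sentence covers time to maximum Grade 3/4, so that summary is optional in the SAP as well, although the protocol commits to it too.

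SAP Section 6 states: "There have been no changes to the initially planned analyses as of the finalization of this SAP".

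**The concern.** The SAP changes two things. It adds a second, easier way to be counted as resolved, and it turns a planned summary into one that might not be produced. Protocol 11.5 leaves detailed methodology to the SAP, but a new criterion that can be met while the patient is still above baseline changes the definition rather than filling in detail.

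What is at stake is how the reversibility of Grade 3/4 laboratory abnormalities is read in a study without a control arm. A reader who knows the protocol would take resolved to mean back at baseline grade. Under the SAP, a patient who starts at Grade 0 and remains at Grade 2 indefinitely is resolved.

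**Working it through.** There is no stated figure on this point to reproduce. The check compares the two rules over every possible grade.

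**Is it an amendment artefact?** SAP 3.3 says "A total of approximately 115 patients will be enrolled in the study", which is the Amendment 1 total; Amendment 2 plans about 155. The SAP therefore follows Amendment 1. Amendment 1 already had the baseline-grade definition and the firm commitment, so the SAP departs from both protocol versions and a later amendment does not explain the mismatch.

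**Rules.** Let *b* be the baseline grade and *r* a later grade after a worst grade of 3 or 4 (NCI-CTCAE Version 5.0 in both documents).

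- Protocol: resolved if *r* ≤ *b*.
- SAP: resolved if *r* ≤ 2 or *r* ≤ *b*.

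| Baseline grade | Resolved under protocol | Resolved under SAP | Resolved under SAP only |
|---|---|---|---|
| 0 | 0 | 0, 1, 2 | 1, 2 |
| 1 | 0, 1 | 0, 1, 2 | 2 |
| 2 | 0, 1, 2 | 0, 1, 2 | none |
| 3 (worst grade 4) | 0, 1, 2, 3 | 0, 1, 2, 3 | none |

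No grade is resolved under the protocol but unresolved under the SAP. The SAP set contains the protocol set for every baseline grade and is larger only for baseline 0 or 1. It follows that:

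- the proportion resolved under the SAP is equal to or higher than under the protocol;
- for any one patient, the SAP resolution date is the same or earlier.

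The statement about time is per patient. SAP 5.6.3 does not name an estimator. If times were summarized only among patients who resolve, the SAP rule would also bring extra patients into that group, and the group median need not move in one direction.

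**Size, on assumptions only.** Let *p* be the proportion resolved under the protocol rule, and *f* the share of the remaining patients who reach Grade 2 or lower but stay above baseline. The SAP proportion is *p* + *f*(1 − *p*). The documents give neither *p* nor *f*, so the values below are illustrative.

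| *p* | *f* = 0 | *f* = 0.10 | *f* = 0.25 | *f* = 0.50 |
|---|---|---|---|---|
| 40% | 40% | 46% | 55% | 70% |
| 60% | 60% | 64% | 70% | 80% |
| 80% | 80% | 82% | 85% | 90% |

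For example, with *p* = 0.60 and *f* = 0.25: 0.60 + 0.25 × 0.40 = 0.70. With *f* = 0 there is no difference at all.

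**The case against.** The strongest reply is that little depends on this. The summary is descriptive and optional under the SAP. SAP 5.6.3 also commits to visit-level summaries, shift tables from baseline to worst grade, and by-patient listings of all laboratory data. That stands and keeps the point minor. The listings would show a patient still at Grade 2, though the shift tables would not, because they stop at the worst grade.

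A second reply is that the threshold has precedent. Protocol Table 9 uses Grade 2 or baseline as the recovery level for Grade 4 neutropenia, and Table 8 of Amendment 1 used Grade 2 for phosphorus. These are dose-management rules, and others in the same protocol (Table 6, and Table 9 for anemia and thrombocytopenia) use Grade 1 or baseline. The precedent may explain where the phrase came from. It does not settle the analysis definition, which Protocol 11.5.4 states outright.

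Two stronger readings are tempting, and the documents support neither.

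- A reader might infer that reversibility is in fact overstated, or that resolution will often come earlier. That depends on how many Grade 3/4 patients start at Grade 0 or 1 and are seen above baseline at Grade 2 or lower, which the documents do not give.
- A reader might infer that hyperphosphatemia would carry two resolution times in one report, with the laboratory one systematically shorter, because SAP 7.5 measures adverse events of special interest by the "longest time from onset to complete resolution or improvement to the grade at baseline". Those times come from adverse-event records merged into clusters, taking the longest cluster and applying their own censoring rule. Under Protocol 9.3.1 a laboratory abnormality becomes an adverse event only if it has clinical impact and does not belong to a diagnosis already reported. The two times would differ even with identical grade thresholds. Nor do the documents show that phosphorus receives a numeric CTCAE laboratory grade: Amendment 1 supplied its own phosphorus grades, and Amendment 2 removed them.

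**Conclusion.** The mismatch is real, undeclared and present against both protocol versions. Its direction is certain: measured by the protocol's definition, the SAP rule can raise the proportion resolved and shorten a patient's time to resolution, and can never do the reverse. It acts only on patients with baseline Grade 0 or 1. The size cannot be derived from the documents and could be zero. The conclusion assumes that both rules are applied to the same graded laboratory values in the same patients.

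The point is minor. It concerns the definition behind one descriptive laboratory safety summary and whether that summary is produced. It says nothing about any dosing or resumption rule.

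**What to change.** In SAP 5.6.3, delete the Grade 2 alternative so that the definition matches Protocol 11.5.4, and replace the optional wording with the protocol's firm commitment, for both time to resolution and time to maximum Grade 3/4.

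If return to Grade 2 or lower is also of interest, add it as a separate measure labelled improvement to Grade ≤ 2 and record the addition in SAP Section 6.

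The cost is one phrase and one verb in the SAP, plus a line in Section 6 and one more table if the extra measure is kept. No new data are needed, since the same graded laboratory results serve both definitions.
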